## PROJECT SUMMARY

### Title

Evaluation of the Effect of a Hydroxyapatite-Forming Desensitizing Agent on Postoperative Sensitivity in Composite Restorations

### INTRODUCTION AND GENERAL INFORMATION

Nowadays, both esthetic concerns and ecological awareness have led to the preference of composite resin instead of amalgam in most restorations. However, the acidic adhesive monomers used during the application of composite resins can cause pain following restoration. This type of pain, defined as postoperative sensitivity, generally occurs independently of restoration failure and is reported by patients at different levels and intensities. Typically, this pain lasts for a period of several days to one month after the restoration and then subsides. In rare cases where severe pain occurs, endodontic treatment may become necessary (1).

Postoperative sensitivity may arise due to several factors, including the remaining dentin thickness, the diameter and patency of dentin tubules after acid etching, the general condition of the pulp, and clinician-related factors (2). To reduce postoperative sensitivity, several approaches have been suggested, such as avoiding excessive drying during cavity preparation (3), applying desensitizers and liners to the cavity (2), and using self-etch adhesives (4). However, current evidence shows that the type of adhesive itself is not a determining factor for postoperative sensitivity (5). It has also been reported that desensitizers applied to the cavity may influence bond strength. Therefore, careful selection of the material to be applied is important for the success of the restoration.

Teethmate Desensitizer (Kuraray Noritake), a desensitizing agent containing tetracalcium phosphate and dicalcium phosphate anhydrous, forms hydroxyapatite through a dissolution-precipitation reaction. An in vitro study demonstrated that this material does not adversely affect bond strength (6). Another in vitro study (7) reported that while Teethmate Desensitizer reduced adhesive bond strength, it also decreased microleakage. For this reason, it was suggested that in multimode adhesives used in self-etch mode, Teethmate Desensitizer could be applied to the cavity before adhesive application in order to reduce postoperative sensitivity.

Although the effectiveness of Teethmate Desensitizer in occluding dentin tubules and reducing sensitivity has been reported in clinical studies (8–10), no study investigating its effect on postoperative sensitivity following composite resin restorations has been identified.

Based on literature review, the aim of this phase IV study is to evaluate the effects of Teethmate Desensitizer, when applied under composite restorations, on postoperative sensitivity compared with a control group.

## MATERIALS AND METHODS

This study will be conducted in three phases. In the first phase, sample size calculation was performed using statistical methods.

### Statistical Pre-analysis:

The sample size was calculated using the online calculator at [www.sealedenvelope.com](http://www.sealedenvelope.com). Assuming a power of 90% and an error margin of 5%, the required number for each group (experimental and control teeth) was found to be 43. Since a split-mouth design will be used, in which each patient will have both experimental and control groups, the required number of participants was also determined to be at least 43. Considering possible dropouts during the study, the final sample size was set at 50 participants. Randomization will be achieved using a blocked randomization technique at [www.sealedenvelope.com](http://www.sealedenvelope.com). For blocked randomization, the seed number will be set as 12345 and block size as 2.

In the second phase, volunteer participants will be selected among patients who apply to the Faculty of Dentistry, Başkent University, and are referred to the Department of Restorative Dentistry for treatment after clinical and radiological examination revealed carious lesions. The inclusion criteria will be as follows:

- Voluntary acceptance of participation in the study
- Age between 18–65 years
- Presence of at least 12 teeth in occlusion
- The teeth to be included must have natural antagonists and adjacent teeth (normal occlusion)
- Anterior or posterior teeth with primary or secondary carious lesions in which the cavity preparation is expected to approach the pulp closely but without pulpal exposure
- Each participant must have two teeth, one on the right and one on the left, fulfilling the above criteria
- Absence of any other factor causing sensitivity or pain that might interfere with evaluation

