## STATISTICAL ANALYSIS

Measurements will be obtained from two paired teeth of the same patient. The VAS and NRS values of these paired groups will be compared. For this purpose, chi-square test will be used for NRS values, and independent two-sample t-test will be used for VAS values. The significance level will be set at  $p = 0.05$ .

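### The 90% power is not shown to apply to this split-mouth trial: 43 per group becomes 43 participants with no paired basis, outcome or difference stated

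*Combined protocol and SAP*

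**What the plan says.** All the sizing text is in the Statistical Pre-analysis section of Materials and Methods.

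- Source: "The sample size was calculated using the online calculator at" a named website. The calculator module and the type of outcome are not given.
- Error rates: "Assuming a power of 90% and an error margin of 5" per cent. Sidedness is not given.
- Result: "the required number for each group (experimental and control teeth) was found to be 43".
- Step to participants: the presence of both arms in every mouth is the one reason offered for concluding that "the required number of participants was also determined to be at least 43".
- Allowance for loss: "Considering possible dropouts during the study, the final sample size was set at 50 participants". No dropout rate is given.

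The Statistical Analysis section says "Measurements will be obtained from two paired teeth of the same patient". It then plans a chi-square test for NRS and an independent two-sample t-test for VAS, at p = 0.05.

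Neither section gives an effect size, an SD, event rates, an endpoint or time point for sizing, a within-patient correlation, or an SD of the within-patient difference.

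**The concern.** The precision of a split-mouth comparison depends on the SD of the difference between a patient's two teeth. That SD depends on the correlation between the teeth. A per-group number for separate groups carries over unchanged to pairs only if the correlation is zero, whereas a split-mouth design is normally chosen because a positive correlation is expected. The only reason the plan gives for 43 participants is a count of teeth: one per arm from each patient.

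This is the plan's only power statement, and it is tied to no scale, time point or difference. If the result is not significant, readers cannot tell what difference it makes unlikely. It could be cited as showing no effect at 90% power, and the documents would not support that.

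**Working it through.** **Inputs from the documents.** Power 90%; error 5%; 43 per group; 43 participants; 50 after the allowance for loss. The allowance is consistent: 1 - 43/50 = 14% loss.

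**Assumed, because the documents do not say.** Two-sided test; continuous outcome with equal SDs; correlation rho between a patient's two teeth from -0.3 to 0.7; per-tooth VAS SD of 20 mm, used only for the mm illustration.

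**1. Can the 43 be reproduced?** Not without an effect size. It can be back-solved. For two independent means,

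n per group = 2(1.960 + 1.282)² / d² = 21.01 / d².

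Setting n = 43 gives d = 0.699, and d = 0.70 gives n = 42.9, rounded up to 43. So 43 fits a two-group calculation at about 0.70 SD. If one-sided, it fits about 0.63 SD.

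The solution is not unique. For a binary outcome, n = 10.507[p1(1 - p1) + p2(1 - p2)] / (p1 - p2)². Rounded up, this also gives 43 for 30 pairs of whole-percentage rates from 0 to 100%, such as 52% v 20% (42.03), 40% v 11% (42.2) and 20% v 0% (42.03). The outcome behind the 43 therefore cannot be identified.

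**2. What does d = 0.70 imply for pairs?** The SD of the difference is SD × sqrt(2(1 - rho)), so the standardised paired effect is dz = d / sqrt(2(1 - rho)). The approximate number of pairs is the per-group number times (1 - rho). Exact power is from the noncentral t distribution with 42 degrees of freedom.

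| rho | dz | Paired t-test power, 43 pairs | Pairs needed for 90% |
|---|---|---|---|
| -0.3 | 0.434 | 79% | 58 |
| 0 | 0.495 | 88.7% | 45 |
| 0.3 | 0.592 | 96.6% | 33 |
| 0.5 | 0.700 | 99.4% | 24 |
| 0.7 | 0.904 | >99.9% | 15 |

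At rho = 0 the normal approximation returns 90% with 43 pairs; the shortfall to 88.7% comes from using the t distribution. With 50 pairs, power is 93% at rho = 0 and 99.8% at rho = 0.5.

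**3. What does the planned VAS test do?** An independent t-test was simulated on 43 correlated pairs at about 0.70 SD (100,000 runs per setting).

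| rho | Power | True type I error (nominal 5%) |
|---|---|---|
| 0 | 89% | 5.0% |
| 0.3 | 93% | 2.1% |
| 0.5 | 96% | 0.7% |

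At rho = 0.3 or 0.5, neither the 90% nor the 5% describes the test as planned.

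**4. What can be said without knowing d?** A paired t-test has 90% power at two-sided 5% for a mean difference of 0.506 SD of the difference with 43 pairs, or 0.468 with 50. In mm this is dz × 20 × sqrt(2(1 - rho)) at the assumed per-tooth SD:

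| rho | 43 pairs | 50 pairs |
|---|---|---|
| 0 | 14.3 mm | 13.2 mm |
| 0.5 | 10.1 mm | 9.4 mm |
| 0.7 | 7.8 mm | 7.2 mm |

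**The case against.** The strongest reply is that nothing has gone wrong in practice. At zero correlation the carry-over is essentially right: 88.7% for the paired test, against 89.4% for an unpaired t-test with 43 per group at 0.70 SD. At positive correlation it is conservative, and the planned 50 add margin. The sizing also uses the same unpaired frame as the planned t-test for VAS, so the deeper conflict is between the design and the analysis. Finally, the documents name a website but no module, so a two-group calculation is an inference from the per-group wording and not a stated fact.

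All of this stands, and it rules out three stronger readings that a reader might draw:

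- *The trial is underpowered.* The carry-over does not show this; it costs power only if the two teeth are negatively correlated, and nothing in the documents suggests that. Power could be low if the true effect were much smaller than 0.70 SD, for instance if most scores were zero. But two separate groups of 43 would have the same problem, so this is no evidence against the carry-over.
- *The 90% is wrong.* Without the inputs it can be neither confirmed nor refuted.
- *The 90% belongs to neither the VAS nor the NRS comparison.* Several sets of inputs give 43, so the target is unidentified. The 43 may well have been meant for VAS.

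The reply does not supply the missing basis. Agreement between the sizing and an unpaired test is no defence when the Statistical Analysis section itself calls the teeth paired.

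**Conclusion.** The concern holds as a fault in the basis of the power statement. The step from 43 per group to 43 participants uses no correlation and no SD of the paired difference, and the 90% is attached to no outcome or difference. It is therefore not shown to be the power of this paired trial.

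On the assumption of a two-sided, two-group calculation at about 0.70 SD, the paired power with 43 pairs is 88.7% at correlation 0, 96.6% at 0.3 and 99.4% at 0.5, with 79% at -0.3. For positive correlation, then, the plan errs on the safe side and needs no more patients. The practical harm lies in interpretation: a null result has no stated difference to be read against. The independent t-test adds to it, being conservative when the correlation is positive. The power and type I error figures in this point rest on the back-solved 0.70 SD, where an effect enters, and on the assumed correlations; the mm figures rest also on the assumed SD of 20 mm.

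**What to change.** Keep 50 participants and make these changes together.

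1. In the Statistical Pre-analysis, state what was entered into the calculator (module, outcome type, difference and SD or rates, sidedness), and name the endpoint and time point that the sizing serves.
2. Delete the inference from 43 per group to 43 participants. Replace it with a paired statement for VAS, for example: 43 evaluable pairs give 90% power (paired t-test, two-sided 5%) to detect a mean within-patient difference of 0.51 SD of the difference; with 50 pairs the figure is 0.47. Give the mm equivalent over a stated range of per-tooth SD and within-patient correlation.
3. In the Statistical Analysis section, change the independent t-test for VAS to a paired comparison. Without this, the new power statement would describe a test that the plan does not run.
4. Report the mean within-patient VAS difference with its 95% CI, and read a null result against the stated mm figure.

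The cost is protocol wording and about an hour of calculation, with no extra patients. The stated power becomes conditional on named assumptions. If recruitment has already ended, items 3 and 4 are still worth doing: the interval shows which differences the data are compatible with, whatever the planning figure was.

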### Exclusion criteria:

- Refusal to participate in the study
- Age under 18 or over 65 years
- Presence of dental or orofacial pain
- Presence of bruxism
- Presence of advanced periodontal disease
- Presence of systemic diseases that may hinder treatment procedures or follow-up visits
- Teeth with excessive loss of tooth structure requiring full crown restoration, or with severe attrition, cracks, or non-vital teeth
- Pulpal exposure during cavity preparation
- Presence of gingival recession
- Use of analgesics, anti-inflammatory, or psychotropic drugs within the last 15 days or currently using them
- Pregnancy or lactation
- Known allergy to the materials to be used

Eligible individuals will be invited to participate in the study after verbal explanation

of the purpose and methodology. Participation will be voluntary, and those who accept will sign an Informed Consent Form. If deemed necessary, participants will receive oral hygiene motivation, and interventions will begin once oral hygiene has reached a satisfactory level.

In the third phase, before starting treatment of the teeth diagnosed with caries through clinical and radiological examination, vitality tests will be performed. After cavity preparation of two teeth per participant, the cavities will be isolated. At the point closest to the pulp, a calcium hydroxide-based pulp capping agent (Dycal, Dentsply Sirona, York, USA) will be applied in paste form. Subsequently, Teethmate Desensitizer will be applied according to the manufacturer's instructions to one cavity randomly, while the other will receive no desensitizer. To ensure randomization, pre-prepared allocation lists from [www.sealedenvelope.com](http://www.sealedenvelope.com) will be placed in opaque envelopes, which will be opened only at the time of intervention.

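### The protocol prints the randomisation seed and block size and does not separate the single operator from the list, so the opaque envelopes alone do not secure concealment

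*Combined protocol and SAP*

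**What the plan says.** All references are to the combined protocol and SAP.

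- **Generator and settings (Statistical Pre-analysis).** "Randomization will be achieved using a blocked randomization technique" on a named website, and then: "For blocked randomization, the seed number will be set as 12345 and block size as 2".
- **Size and unit (same section).** "the final sample size was set at 50 participants". The groups are described as teeth: "the required number for each group (experimental and control teeth) was found to be 43". "Each participant must have two teeth, one on the right and one on the left, fulfilling the above criteria".
- **Eligibility (same section).** It depends on a judgement made before treatment, that "the cavity preparation is expected to approach the pulp closely but without pulpal exposure".
- **Concealment (treatment text below the Exclusion criteria list).** "To ensure randomization, pre-prepared allocation lists from" the same website "will be placed in opaque envelopes, which will be opened only at the time of intervention". That text describes preparation of both cavities, isolation and the calcium hydroxide liner first, and then the desensitizer in one cavity and nothing in the other.
- **Roles (restoration and follow-up text of Materials and Methods).** A single operator does all restorations. Participants record daily pain for each tooth, and a different dentist evaluates the restorations at follow-up.

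No section says who generates the list, who fills or holds the envelopes, whether they are sealed, numbered or used in sequence, or that the operator has no access to the list or its settings. The block unit (participants, or the two teeth of one participant) is not stated either.

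**The concern.** A seed is set so that a list can be reproduced. Recording it for audit is good practice. Printing it in the protocol that the treating team works from, beside the generator and the block size, makes reproduction available to the person from whom the allocation should be hidden. An opaque envelope hides its contents only from someone who cannot obtain them another way.

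The Introduction names remaining dentin thickness and clinician-related factors among the causes of postoperative sensitivity. A split-mouth design balances what belongs to the patient, but not differences between the two teeth or in how each is handled. With foreknowledge of the side, two stages before the envelope is opened are exposed: the choice of tooth pair, which rests on expected depth, and the preparation and lining of each cavity.

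**Working it through.** **Inputs.** Number of participants 50, seed 12345 and block size 2, all from Statistical Pre-analysis. There is one right/left allocation per participant, because each contributes one experimental and one control tooth. The seed and block size are settings, so there is no computed figure of the plan to reproduce; the 50 is taken as given.

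**Step 1: who could know the list.** The operator learns each allocation on applying it, because the control cavity receives no desensitizer. The only separation of roles in the text is the second dentist, which protects assessment and not the list.

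**Step 2: what rebuilding the list needs.**

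| Needed | In the documents? |
|---|---|
| Generator | Yes, named |
| Seed | Yes, 12345 |
| Block size | Yes, 2 |
| List length and group labels | No |
| Mapping of label to right or left tooth | No |
| Same list returned for the same settings | Assumption; the website was not tested |
| Envelopes used in list order | Not stated |

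The printed text alone is therefore not enough. A team member who knows the remaining settings and the mapping faces one list. Under the last two conditions, that person could know up to 50 of 50 allocations (100%) before any envelope is opened. This holds whichever block unit was used.

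**Step 3: the block size without rebuilding the list.** Suppose the seed is unknown but past allocations are seen and envelopes follow list order.

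- *Blocks of 2 across participants.* There are 50 / 2 = 25 blocks and 2^25 = 33,554,432 possible lists. The first allocation of each block is a coin toss and the second follows from it. Certain: 25 of 50. Correct on best guess: 25 + 25 × 0.5 = 37.5 of 50 (75%).
- *Block is one participant's two teeth.* The order within each pair is a fresh coin toss. Certain in advance: 0 of 50. Correct on best guess: 50 × 0.5 = 25 of 50 (50%), which is chance. This is already simple randomisation of side.

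The description of the groups as experimental and control teeth favours the second reading, but the text does not settle it.

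**Step 4: effect of withholding the seed alone.** Under the tooth-pair reading, predictability falls from 100% to 50%, which is full concealment. Under the across-participant reading it falls only to 75%, so the block would have to change too.

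**The case against.** The strongest reply is that the plan has real safeguards and shows no breach. Envelopes are opaque and opened only at intervention, and the order of steps places allocation after preparation and lining. Each participant is their own control, pain is recorded by the participant, and another dentist evaluates. No section says that the operator chooses the tooth pairs. The adhesive, composite and finishing steps follow with the allocation known whatever is done about the seed. A printed seed also makes the list auditable.

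Most of this stands, and it limits the consequence. It does not remove the gap: none of these features conceals allocation from an operator who can obtain or rebuild the list, and auditability needs the seed to be archived, not printed.

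Three stronger inferences are tempting, and the documents do not support them.

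- *That allocation was in fact known in advance.* The text shows an opportunity only.
- *That anyone with the protocol could rebuild the list.* List length, labels and mapping are not printed, repeatability of the generator was not tested, and envelope order is not stated. For the same reason, no count of predictable allocations can be derived from the printed text alone.
- *That a block size of 2 gives away half the allocations.* This is true only if blocks run across participants, which the wording does not favour.

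**Conclusion.** The point holds as a gap in allocation concealment, of minor severity and cheap to close. The method as written, and not merely a missing detail, weakens the envelopes, because the settings are disclosed and nobody is named to keep the list from the operator.

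The upper bound is 50 of 50 allocations known in advance. It rests on three conditions: the generator repeats the list, the envelopes follow list order, and the person knows all settings and the label-to-side mapping. The figures of 25 certain and 37.5 correct apply separately, and only to blocks across participants. The effect of any foreknowledge on the pain comparison cannot be sized from the documents. The exposure that can be removed is confined to tooth-pair selection, cavity preparation and lining.

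**What to change.** 1. Replace the printed seed with a new, undisclosed one. An existing team member who is neither the operator nor the evaluating dentist generates and holds the right/left list and archives the seed for audit.
2. Use sealed, sequentially numbered opaque envelopes. State that each is opened only after both cavities are prepared and lined, which makes the implied order explicit.
3. State the block unit. If it is the tooth pair, no change is needed. If blocks run across participants, use simple randomisation of side per participant.
4. The protocol gives study dates of May 2021 to May 2022. If enrolment has begun or ended, apply items 1 to 3 to any remaining participants, and report who generated the list and whether the operator had access to it.

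**Cost.** A few sentences of protocol text and a few minutes of a team member's time. Items 1 and 2 have no statistical downside. The change in item 3, where it applies, means that right/left counts are no longer fixed at 25/25. The number of experimental teeth on the right would follow Binomial(50, 0.5), with SD √(50 × 0.25) = 3.54, and about 97% of lists would have 18 to 32 of 50 on the right.

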When necessary depending on cavity type, a matrix system (Mylar strip, sectional matrix, or Tofflemire) will be applied before restoration. All cavities will be treated with a one-step self-etch adhesive (Clearfil SE Bond, Kuraray Noritake, Tokyo, Japan) according to manufacturer's instructions and light-cured with an LED unit (LedMax Cordless 550, Benlioğlu Dental, Ankara, Turkey) at a constant intensity  $>1,500$  mW/cm^2 for 10 seconds. Restorations will be completed using a universal composite resin (Filtek Z250, 3M Espe, St. Paul, MN, USA) with the oblique incremental technique. Each increment of composite will be polymerized for 20 seconds with the same LED device. Finishing and polishing will be performed using diamond finishing burs, polishing rubbers, and disks (Soflex, 3M Espe, St. Paul, MN, USA). All restorations will be performed by a single operator.

After restoration, participants will be given two forms (one for each tooth) to record their daily pain levels for one week. Instructions for filling out the forms will be provided. The forms will include the Numerical Rating Scale (NRS, 0–4) and the Visual Analog Scale (VAS, 0–100 mm). One week later, patients will return for follow-up, and the completed forms will be collected. Six weeks after the restorations, patients will return for another follow-up. At both the one-week and six-week follow-up visits, restorations will be evaluated by another dentist to ensure double blinding.

At the one-month control visit, tooth vitality will first be assessed. If the tooth is vital, postoperative sensitivity will be evaluated using VAS scores and by applying a cold spray (Ice Spray, Picdare S.p.A, Casnate con Bernate, Italy) with a cotton pellet to the mid-buccal surface of the teeth for 5 seconds.

Study Start Date: May 3, 2021

Study Completion Date: May 3, 2022

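### The unit of the block of 2 and the mapping to right or left tooth are undefined; if blocks span patients, 25 of 50 allocations are predictable

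*Combined protocol and SAP*

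**What the plan says.** Under Statistical Pre-analysis the plan states: "Randomization will be achieved using a blocked randomization technique". It then sets the seed and "block size as 2". The same section describes the design ("Since a split-mouth design will be used, in which each patient will have both experimental and control groups"), requires one right and one left tooth per person ("Each participant must have two teeth, one on the right and one on the left, fulfilling the above criteria"), and sets the sample at 50 participants.

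The third-phase text, printed under Exclusion criteria, describes cavity preparation in both teeth, then the liner, then the desensitizer given "to one cavity randomly, while the other will receive no desensitizer". The allocation lists "will be placed in opaque envelopes, which will be opened only at the time of intervention". The restoration text that follows adds: "All restorations will be performed by a single operator". Blinding is claimed only through a different dentist at the follow-up visits.

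The plan does not state four things: whether a block is two patients or one patient's two teeth, how a list entry identifies the right or left tooth, when tooth order is fixed, and who opens the envelope.

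**The concern.** A fixed block of 2 has only two possible orders, so its first entry determines its second. Anyone who knows the block size and sees the first allocation knows the next one before the envelope is opened. The block size is in the protocol, and the person placing the desensitizer can hardly avoid seeing the allocation.

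This matters because choosing the teeth, excavating, placing the liner and applying the pulp-exposure exclusion all come before the allocated step, and all are in the operator's hands. The Introduction itself names remaining dentin thickness and clinician-related factors among the causes of postoperative sensitivity. Pairing removes differences between patients. It does not remove differences between the two teeth that arise because the operator already knows which one will be treated.

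**Working it through.** The plan gives no figure for predictability, so there is none to reproduce. The inputs are the block size (2), the number of participants (50) and the 1:1 split within each patient, all from Statistical Pre-analysis. That the operator sees each allocation is inferred from the procedure.

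**Reading A: a block is two consecutive patients, and an entry gives the side treated.**

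There are 50/2 = 25 blocks. The second patient in each is fully determined, so 25 of 50 allocations are known in advance. The other 25 are coin tosses. Expected correct guesses are 25 × 1 + 25 × 0.5 = 37.5, and 37.5/50 = 75%.

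For a general block of 2m, suppose the guesser names the side used less often so far and tosses a coin when tied. The expected share correct is [m + (4^m / C(2m, m) − 1)/2] / (2m).

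| Block size | Calculation | Share correct |
|---|---|---|
| 2 | [1 + (4/2 − 1)/2]/2 | 0.750 |
| 4 | [2 + (16/6 − 1)/2]/4 | 0.708 |
| 6 | [3 + (64/20 − 1)/2]/6 | 0.683 |
| 8 | [4 + (256/70 − 1)/2]/8 | 0.666 |
| Independent draws | – | 0.500 |

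A simulation of 20,000 trials of 50 patients gave 0.750 for blocks of 2, 0.703 for blocks of 4, 0.679 for blocks of 6 and 0.500 for independent draws. The values for 4 and 6 fall slightly below the formula because 50 is not a multiple of either, so the last block is incomplete. Larger blocks therefore help only in part.

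None of these figures depends on the seed. The guesser uses only the block size and the allocations already opened.

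**Reading B: a block is the two teeth of one patient.**

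The 50 blocks are then 50 independent fair draws, and nothing carries over from one patient to the next. The second tooth is the complement of the first under any split-mouth scheme. What remains is how first and second are tied to right and left. Suppose an operator prefers one particular tooth of each pair to receive the agent. The preferred tooth is treated in:

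- 50% of patients if a written rule fixes the order (for example, first entry = right tooth);
- 50% if the operator names the first tooth while the envelope is still closed;
- up to 100% only if the order can be set after opening.

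**Cost of dropping the blocks.**

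Each patient contributes one tooth to each arm, so the arms stay equal whatever sides are drawn. Only the right/left split can vary. With k right-side treatments in n patients, the expected efficiency loss when side is modelled is E[((2k − n)/n)²] = 4·(n/4)/n² = 1/n = 1/50 = 2%.

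**The case against.** A reader might infer that a block of 2 breaks concealment on any reading: either every second allocation is known, or the operator decides which tooth counts as first and so has all 50 choices open. The documents do not support that. They are silent on tooth order; they do not hand it to the operator, and the text says that the cavity receiving the agent is chosen at random. A fixed right/left rule, or an order recorded before opening, would keep concealment intact. Under Reading B the block of 2 is also what gives each patient one treated and one control tooth, so it cannot be called useless there. Reading B is plausible, because the sample-size text describes the groups as teeth.

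Two further points stand. First, 75% measures predictability, not bias in VAS or NRS. Foreknowledge cannot steer a patient to one arm; it can act only through tooth choice, preparation or exclusion. Patients record their own pain, and another dentist evaluates the restorations. Second, the plan does not say in terms that envelopes are opened after both cavities are prepared. That is the natural reading of "will be placed in opaque envelopes, which will be opened only at the time of intervention", but the same section also uses the word intervention for treatment as a whole.

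These points limit the conclusion but do not remove it. A different dentist at follow-up does not protect decisions made before the envelope is opened, and nothing in the plan excludes Reading A.

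**Conclusion.** The point holds conditionally. The plan fixes a block size of 2 without defining the randomisation unit or the tooth mapping.

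- If blocks span patients, 25 of 50 allocations are predictable and expected correct guessing rises from 50% to 75%. This assumes that the operator knows the block size, sees each allocation and takes the envelopes in list order.
- If the block is the tooth pair, there is no predictability between patients. Concealment then depends only on a rule, not stated, that fixes tooth order before opening.

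The general conclusion that concealment fails does not follow from the documents. No size can be put on any resulting bias in the pain scores. The printed seed ("the seed number will be set as 12345") is a separate weakness; changing it would resolve neither branch. The change is worth making because it is cheap and settles both.

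**What to change.** Replace the block size of 2 with one independent, unblocked 1:1 draw per patient of the side that receives Teethmate. Put each result in one sequentially numbered opaque envelope naming right or left. State who holds and opens the envelopes, and that each is opened only after both cavities are prepared and found free of pulp exposure. This removes the predictability under Reading A and the mapping gap under Reading B.

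The cost is one regenerated list of 50 and a few changed sentences in Statistical Pre-analysis and the third-phase text. Right and left may not split exactly 25/25, with the 2% expected loss shown above if side is modelled and none otherwise. If patients have already been treated under the present scheme, report which unit, mapping and opening time were used.
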